#### **F.1.b. Follow-up Encounters**

Study staff will conduct phone calls or email communications at 2 and 6 weeks to confirm contact information and inquire about discharge follow-up. Patients will be given an appointment day and time prior to discharge for the first phone contact at 2 weeks. Any specific medical concerns reported during any call will be forwarded to the primary provider. At 12 and 24 weeks, HbA1c is measured and the staff will assess outpatient follow-up, hospital readmission or emergency department visit, adherence to insulin and glucose monitoring, hyperglycemic and hypoglycemic events, and perform the DES-SF.

### **F.2 Discharge Order Set group**

#### **F.2.a Discharge**

As with the ESC group, the discharge regimen will be determined by the primary team with assistance from the diabetes service if requested. Hospital discharge is also coordinated by the primary team and existing patient care resource manager who arranges follow-up prior to discharge. A discharge summary is sent to the primary provider per routine practice. Patients are instructed to maintain a glucose and insulin diary. Patients will receive survival skills education by a dedicated nurse.

In addition to these elements, for the DOS group the primary team will be contacted to complete the Diabetes Discharge order set, which will be pre-populated into the electronic discharge navigator. The discharge order set contains a variety of elements that are intended to ensure a clear/complete communication to the patient and outpatient provider (summarized in Table 8, detailed mock-up provided in Appendix 1). In particular, the instructions facilitate identifying an appropriate diet, establishing timely and effective follow-up and ordering clear and complete prescriptions. The standardized instructions provide guidance to the patient for monitoring and interpreting glucose levels as well as a basic summary of survival skills.

**Table 8. Diabetes Order Set Summary**

Standard Elements		
Diabetes-specific elements	Detail	Prescriber Guidance
Diet	Choice of consistent (defaults to 45 or 60 gram/meal) or flexible carbohydrate	Selection criteria for flexible carb diet.
Follow-up and referrals	Choice of primary care or endocrinology (call for appointment for *** weeks, appointment has been made for ***) Diabetes education (general education or survival skills)	Only local patients should be referred to OSU.
Patient instructions	Call provider for hypoglycemia Call provider for hyperglycemia Bring glucose log to appointment Glucose targets Home diabetes management attachment	Identification of glucose targets
Insulin prescriptions	Each insulin is presented as a panel, linked to pen needle or syringe as appropriate Each insulin Rx defaults to 3 pen or 1 vial with 1 refill Insulins categorized by basal, prandial set meal dose with correction, or prandial flexible meal dose with correction	Number of units per pen or vial Syringe size Titration options for basal insulin Selection criteria for flexible meal dosing Correction dosing from pick list of low, standard, or high doses
Glucose Monitoring supplies	Panels categorized by frequency of monitoring Each panel contains glucometer, test strips, lancets, alcohol wipes Prescriptions default to dispense appropriate number of supplies with 1 refill	Guidance on monitoring frequency
Other DM supplies	Ketone strips Glucagon	Selection criteria provided for each

### **F.2.b. Basal insulin titration**

The patient will receive instructions via the discharge order set and nurse to adjust the U300 basal insulin dose 2 unit Q4 days for glucose >130 mg/dl, provided no values <80 mg/dl.

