## **Summary and Future Directions**

For the hospitalized patient, multiple factors collude to impede successful transitions in care in the current fragmented health system. Diabetes provides a suitable framework for chronic disease management in general due to its complexity regarding therapies, self-care, and multiple comorbidities. This proposal seeks to redefine the role of diabetes management throughout the continuum of care. Future applications would include multi-center studies and studies to determine the efficacy of the individual components.

Appendix: Diabetes Discharge Orderset		➤ Drop-down Choices
Diet — Note: Most patients will require consistent carbohydrate diet		
➤ Consistent carbohydrate diet Note: appropriate for most patients, including those discharging to skilled nursing		 45 grams per meal  60 grams per meal
 Flexible carbohydrate diet Note: carbohydrate counting method, only if patient using prior to hospitalization or has demonstrated competency		
Follow-up		
➤ Primary Care Provider	[see below]	
➤ Endocrinologist Note: If patient does not live near Columbus, please locate an Endocrinologist nearest to their home. The phone number for OSU Endocrinology is [contact]	 Call for an appointment. You should be seen within 2 weeks of discharge from the hospital, your diabetes medications may need adjustment  Call for an appointment. You should be seen within *** weeks  You have a follow-up appointment with *** on [date]	
➤ Diabetes Education Note: If patient does not live near Columbus, please locate a diabetes educator nearest to their home. The phone number for OSU Endocrinology is [contact]	 Survival skills  General diabetes education	
 Bring a blood sugar log (record of your glucose readings), medications and glucose meter with you.		
Notify Physician		
 Call your healthcare provider if you are having recurrent low sugars (less than 70 mg/dl) more than 2 days in a row or if you have any severe low sugars requiring the assistance of someone else to treat.		

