 Call your healthcare provider if you have recurrent high (above 250 mg/dl) blood sugars for more than 3 days in a row, or if you have glucose readings over 250 mg/dl with new symptoms such as nausea, vomiting, or dizziness.		
Patient Instructions		
 Your target glucose is *** mg/dl fasting and under *** mg/dl nonfasting  <Note: Typical blood sugar goals for many people are 80-130 mg/dl in the mornings (fasting) and less than 180 mg/dl throughout the rest of the day>		
 Instructions for Managing Your Diabetes at Home	[Attachment]	
Diabetes Medication and Supply: Note: U100 Insulin vials contain 1000 units, U100 pens contain 300 unit/pen, glargine U300 contains 450 unit/pen, degludec U200 contains 600 unit/pen, lispro U200 contains 600 unit/pen. [each prescription option is paired with U100 0.3 or 0.5 ML syringe or pen needles as appropriate]		
➤ Basal Insulin	 [Example Drop-down Menu:]  Insulin Glargine 300 unit/ml pen *** units every day.  Increase *** unit every 4 days until AM (fasting) glucose is under *** mg/dl, provided that you have no glucoses under 80 mg/dl, do not go above *** unit per day.	
➤ Glargine U100 Solostar pen and pen needles ➤ Glargine U300 Solostar pen and pen needles ➤ Detemir U100 FlexTouch pen and pen needles ➤ Degludec U100 FlexTouch pen and pen needles ➤ Degludec U200 FlexTouch pen and pen needles ➤ Glargine U100 vial and syringes		

 
➤ Detemir U100 vial and syringes
 
➤ NPH U100 vial and syringes
 
	 [Cardiac surgery patients]: Reduce dose by 2 unit every day that you wake up with a glucose less than 100 mg/dl or if you have any glucose levels under 80 mg/dl.  No titration Dispense: 3 prefilled pens; Refills: 1  Pen needle 31 G x 4 mm For use with insulin once daily Dispense: 50; Refills: 1														

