#### *A.1.c. Potential Risks*

There are no physical risks that would not otherwise be anticipated, as the blood draw for HbA1c is considered standard of care. No specific prescriptive regimen for medications is planned and therefore this also represents standard of care. Furthermore, we already know that this is a high-risk population. Psychological harm may be a possibility if participants neglect other aspects of self-care in favor of diabetes. However, this seems unlikely and will be averted with frequent contact and anticipated increased outpatient follow-up. No financial or legal consequences are anticipated. Breach of confidentiality is a possibility but with standard procedures for immediate entry of paper data into the secure online database, use of a study identification code on all data gathering instruments, and the use of electronic health records, this should be limited.

Other forms of contact, such as internet, could be considered but this would not be a viable forum for all patients. Therefore, email (in secure mail format) will be reserved for follow-up of specific problems or in the event of failure to contact the patient.

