#### **A.3. Potential Benefits of the Proposed Research to Human Subjects and Others**

Participants may benefit from more intensive interaction with study staff, through improved glycemic control as well as close follow-up and anticipatory guidance. Benefits to society include improved glycemic control and hospital readmission, which may result in reduced medical costs, particularly among uninsured individuals. The risks are primarily related to breach of confidentiality and are limited, though still possible. Given the safeguards that are put in place, the potential benefits should outweigh the risks.

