##### **1. Study risk assessment:**

**Exempt** (protocols exempt from IRB review are *not* required to submit a DSMP)

**Level I risk** (identify ***all*** applicable study procedures)

 Anthropometric evaluations	 DEXA scans
 Electrocardiograms (ECG)	 Exercise testing
 Intravenous glucose tolerance tests (IVGTT)	 Intravenous catheter insertion
 Computerized Axial Tomography (CAT) or Magnetic Resonance Imaging (MRI)	 Observational/Behavioral studies
 Oral glucose tolerance tests (OGTT)	 Pathology slide review
 Special or prescribed diets/Nutritional studies	 Venipuncture
 Other low risk non-therapeutic tests or studies (list):	

**Level II risk** (identify ***all*** applicable study procedures)

 Child population	 Normal volunteers using well-described research procedures
 Endoscopy	 Vulnerable population(s), e.g. minorities, indigent, MRDD, prisoners, military personnel, individuals with diminished capacity for decision-making and/or limited literacy skills (e.g. <8 th grade reading level)
 Elderly population	 Pharmaceutical agent(s) under study/Phase IV (post-marketing) studies
 Insulin clamp	 Pregnant population
 Muscle biopsy	 Psych. or neuro. impaired population
 Research-associated procedures (please specify):	
Other moderate risk non-therapeutic tests or studies (please specify):	

The risks for the actual study procedures are considered low as the intervention is limited to behavioral strategy with a blood draw that is otherwise considered to be standard of care. Study-related adverse events, enrollment compliance, proper informed consent, data analysis, confidentiality will be reviewed annually by the study PI and independent safety advocate ([name]).

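### The visible self-titration rule for glargine U300 in the DOS arm only goes up, and the risk statements neither acknowledge the rule nor name hypoglycemia

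*Combined protocol and SAP*

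**What the plan says.** **The assigned rule.** Under F.2.b, the order set and the nurse instruct DOS patients to "adjust the U300 basal insulin dose 2 unit Q4 days for glucose >130 mg/dl, provided no values <80 mg/dl". The U300 panel in the Appendix words this as an increase every 4 days until a fasting target is met, "provided that you have no glucoses under 80 mg/dl, do not go above * unit per day". The prescriber fills in the step, target and cap. Section E makes titration a difference between the arms: standard instructions in DOS, the discharge team's discretion in enhanced standard care (ESC).

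**Reductions.** The panel's other choices are no titration and a box labelled for cardiac surgery patients: "Reduce dose by 2 unit every day that you wake up with a glucose less than 100 mg/dl". That box also applies to any value under 80 mg/dl.

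**Calls.** The Appendix (Notify Physician) asks patients to call for "recurrent low sugars (less than 70 mg/dl) more than 2 days in a row", or for a severe low that someone else must help to treat. Table 8 is shorter: it lists calling the provider for hypoglycemia and gives no threshold.

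**Risk text.** A.1.c: "No specific prescriptive regimen for medications is planned and therefore this also represents standard of care". A.3: "The risks are primarily related to breach of confidentiality and are limited, though still possible". A.5, item 1, rates the procedures as low risk because "the intervention is limited to behavioral strategy with a blood draw that is otherwise considered to be standard of care".

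**The concern.** A patient who follows the rule exactly knows when to go up and when to wait, but not when to come down. The Background section on longer-acting basal insulins gives reasons to care. It expects insulin needs to change after discharge as illness and glucotoxicity resolve, and it calls the feasibility of self-titration in recently hospitalized patients unclear. After a low, the dose then depends on the patient's judgement, a provider contact or the next review.

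The risk text raises a second problem. It treats the medication side as ordinary care with nothing prescribed, while the trial assigns one arm a rule for raising insulin. Patient safety and an accurate risk description are at stake. The treatment comparison is not.

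**Working it through.** The plan gives no figure on this point, so the check is a comparison of texts with a little counting.

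**1. Visible response to each kind of reading**, for a DOS patient without cardiac surgery. Inputs: F.2.b, the Appendix U300 increase line and the Appendix call line.

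| Reading | Next increase | Written reduction | Detailed call line |
|---|---|---|---|
| Above 130 mg/dl, none below 80 | +2 units | none | not triggered |
| One value of 70–79 | held | none | not triggered |
| One value of 54–69, self-treated | held | none | not triggered |
| One value below 54, self-treated | held | none | not triggered |
| Below 70 on more than 2 consecutive days, so at least 3 | held | none | call |
| Low needing another person's help | held | none | call |

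The reduction column is empty throughout. F.2.b uses the neutral verb adjust, but its only trigger is a high value, and the panel that delivers the rule speaks only of increasing. The fourth row matters most because H.2.b uses below 54 mg/dl to define documented symptomatic hypoglycemia.

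**2. Scheduled trial reviews.** Table 9 has contacts at weeks 2, 6, 12 and 24, each with diary and hypoglycemia review. The gaps are:
- 2 × 7 = 14 days
- (6 − 2) × 7 = 28 days
- (12 − 6) × 7 = 42 days
- (24 − 12) × 7 = 84 days

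These count trial contacts only. Clinical follow-up and patient calls come on top.

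**3. A.1.c against the design.** A.1.c says that no specific regimen is prescribed. Section E implements standard titration in the DOS arm, F.2.b fixes the step, interval and thresholds, and A.1.a, in the same Human Subjects part, describes specific dose-titration instructions for the intervention group. These cannot all be right for U300 titration. For the rest of the regimen A.1.c is fair, because Section E and F.2.a leave it to the primary team.

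**4. Hypoglycemia in the risk statements.** It is named in 0 of the 3 (A.1.c, A.3, A.5 item 1). Elsewhere it is a secondary endpoint (H.2.b), an item at every follow-up contact (Table 9) and, when severe, a listed adverse event (A.5 item 2).

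**The case against.** The strongest reply is that the review copy is incomplete. F.2.b delivers the rule partly through the nurse, whose script is not shown. F.2.a calls the Appendix a mock-up, and the home-management attachment is named but not reproduced. Any of these could contain a reduction step. This stands, and it limits the finding to the visible text.

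Real safeguards also exist: the hold below 80 mg/dl, the prescriber's target and cap, the no-titration option, survival-skills education, follow-up arranged before discharge, the call item in Table 8, and nurse contacts. They lower the risk, but none states what to do with the dose after a low. The upward emphasis has a rationale too. The Background says U300 needs about 11–17.5% more insulin than U100, and Section E converts 1:1. That explains why a rule for going up is needed, not why there is none for going down.

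A reader might infer more than the documents support:

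- *That safety oversight overlooks hypoglycemia.* It does not. A.5 item 1 has the investigator and an independent safety advocate review study-related adverse events annually. Item 2 lists severe hypoglycemia, and item 4 compares risks with the actual experience of subjects. Only the risk descriptions omit it.
- *That the dose climbs without limit.* Increases stop at the fasting target, at the cap or after any value below 80 mg/dl, so a count of 4-day steps over 24 weeks would mislead.
- *That a patient may go 84 days without contact.* That figure is only the longest gap between trial reviews.

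**Conclusion.** The concern holds for the visible text, as a safety and consistency point. DOS patients without cardiac surgery have no visible written reduction step, and a single self-treated value below 54 mg/dl brings a hold but no dose decrease and no detailed call instruction. A.1.c is wrong for U300 titration in the DOS arm and sound for the other therapy. None of the three risk statements names hypoglycemia.

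The first conclusion assumes that the nurse script, the built order set and the attachment add no reduction step; if one does, the defect shrinks to carrying it into F.2.b and the panel. The conclusions about the risk text concern those three statements and do not extend to the consent form, which is not in the review copy. Nothing here estimates how often harm would occur. The intention-to-treat primary analysis and the power are unaffected. The change should be made, because it is small and the hazard is a foreseeable one of insulin self-titration.

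**What to change.** 1. **Reduction step.** Check the nurse script and attachment. If they contain a reduction step, carry it into F.2.b and the U300 panel. If not, add one for all DOS patients, for example: *If a fasting glucose is <70 mg/dl, or any glucose is <54 mg/dl, reduce U300 by 2 units, at most once per 4-day period, and make no increase in that period.* The 2-unit size is the sponsor's own, and 70 mg/dl is the order set's own level for a low. The once-per-period limit respects the Background's advice against titrating U300 more often than every 3–4 days. The diabetes team should confirm the thresholds. Keep the existing hold below 80 mg/dl, the target, the cap and, for those patients, the cardiac-surgery box. Reducing after any value below 80 would be too broad: it would cut basal insulin for readings of 70–79 mg/dl and for mild lows caused by meal doses.

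2. **One call rule.** Replace the Appendix call line for lows with: *Call your provider for any value <54 mg/dl, any low needing help, or a second value <70 mg/dl within 4 days.* Replacing the line avoids giving patients competing instructions.

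3. **Risk text.** Replace the A.1.c sentence with: *DOS patients receive an assigned basal insulin self-titration rule whose main risk is hypoglycemia; other therapy, and ESC titration, are left to the discharge team.* Bring A.3 and A.5 item 1 into line.

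**Cost.** An amendment, an order-set edit and some extra calls. The DOS intervention itself changes, and HbA1c may fall slightly less in some DOS patients. A value below 54 mg/dl caused by a meal dose would still lower the basal dose, which the diabetes team should weigh when it confirms the thresholds.

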### **F.2.c. Follow-up Encounters**

The study nurse will contact the patient at 2 weeks and 6 weeks to confirm titration and hospital follow-up. Patients will be given an appointment day and time prior to discharge for the first phone contact at 2 week. Any specific medical concerns reported during any call will be forwarded to the primary provider. At 12 and 24 weeks, HbA1c is measured and the staff will assess outpatient follow-up, hospital readmission or emergency department visit, adherence to insulin and glucose monitoring, hyperglycemic and hypoglycemic events, and perform the DES-SF. Patients are instructed to maintain a glucose and insulin diary.

### **G. Procedures**

Major study procedures and visits are summarized in Table 8.

## H. Data Management and Analysis Plan

### H.1. Data Management

The database used for this study is REDCap, which is a secure web-based application for building and managing data. It is designed specifically for clinical research and administered by the OSU Center for Clinical and Translational Research. Permission for data access or entry will be granted or revoked at a level that is appropriate for each individual involved in the study. Following verification, data will be locked. Data and data labels can be downloaded selectively (for interim progress reports) or in entirety (end of study) directly from REDCap in SAS or Excel format. The study team will record information from the 2, 6, 12, and 24 weeks visits (Table 9).

#### H.1.a. Missing Data

All data analyses will be completed as intention to treat analyses (i.e., individuals analyzed by group according to original random assignment, without regard to adherence to the intervention).

Longitudinal outcomes (e.g., HbA1c) will be analyzed using mixed models utilizing all available measurements from individuals randomized. Missing binary outcomes (e.g., accurate and complete discharge orders, adherence) and missing covariate data will be imputed, using multiple imputation in SAS v9.3 PROC MI.

Table 9. Study Procedures and Visits

Visit number	0	1	2	3	4
Time of Visit	Screen/consent	2 week	6 week	12 week	24 week
Type of visit	In-person	Phone	Phone	In-person	In-person
Informed consent/contact team	x				
Randomization	x				
Load DOS into EMR and inform discharge team	x				
Provide study drug and glucose monitoring instructions	x				
Demographics/Socioeconomic status	x				
Diabetes history	x				
Hospitalization history	x				
PSS scale	x				
DES-SF	x			x	x
Newest Vital Sign	x				
Glucose/insulin diary	x				
Review DOS		x			
Ascertain health care utilization		x	x	x	x
Review glucose/insulin diary		x	x	x	x
Hypoglycemia/Hyperglycemia		x	x	x	x
Review insulin adherence, persistence		x	x	x	x
Nurse counsellor (DOS group only)		x	x	x	x
HbA1c	x			x	x
Fasting blood glucose	x			x	x

DOS=discharge order set, EMR=electronic medical record, PSS=Perceived Social Support scale, DES-SF=Diabetes empowerment scale-short form, In-Person clinic visits will be conducted at either CarPoint East or McCampbell Hall

## H.2. Overview of Analytic Plan

Statistical analyses of these data must not only demonstrate the efficacy of *the discharge order set*, but also estimate effect sizes, examine intervention group differences and identify subgroup differences. Analysis will begin with characterization of the sample with descriptive statistics that identify differences between intervention and control groups (1) evident at baseline, despite randomization, and (2) between groups due to differential attrition. Data will be screened for normality, outliers, and homogeneity. Descriptive statistics will summarize the sample characteristics and distribution of each variable. We will test hypotheses for each aim.

### H.2.a. Statistical Power and Sample Size

The sample size for our study was based on a comparison of change in HbA1c over three months adjusting for baseline covariates related to change in HbA1c: age, whether or not patient is new to insulin, and dose of insulin; the first two were selected based on our preliminary data and the latter was selected based on an expected relationship. The following expression, adapted from Oakes and Feldman, was used to calculate the number of individuals per group:

$$n/group = \frac{4\sigma^2(1-\rho)(1-R^2)(Z_{1-\alpha/2} + Z_{1-\beta})^2}{\Delta^2}$$

where  $\sigma$  is the standard deviation of HbA1c,  $\rho$  is the correlation between baseline and 24 week HbA1c levels,  $R^2$  is the proportion of variability in change in HbA1c explained by the baseline covariates,  $\Delta$  is the difference in change in HbA1c between treatment groups, and  $Z_{1-\alpha/2}$  and  $Z_{1-\beta}$  are standard normal quantiles calculated at the two-sided type-I error rate ( $\alpha$ ) and power (1- $\beta$ ). Using parameter values based on our preliminary data ( $\sigma = 2.2\%$ ,  $\rho = 0.25$ ,  $R^2 = 0.5$ ) and based on the effect observed by Wexler ( $\Delta = 0.8\%$ ), we will need 89 individuals per treatment group with 24 week follow-up to achieve 80% power at  $\alpha = 0.05$ . Since we expect 20% attrition, we will recruit 111 individuals per group into our study. The study is powered to detect a difference in the primary endpoint only. However, additional secondary endpoints of strong interest are pre-specified and included in the analysis.

